8.3.3. Analysis of Primary Efficacy Variable(s)

The efficacy analysis uses the Full Analysis Set and presents data by randomized treatment, unless specified otherwise. Summarization and analysis of the primary efficacy variable will

be performed for the monotherapy cohort (primary cohort), adjunct therapy cohort (for directional investigation, excluding MCP-Mod analysis), and overall.

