5.2. Sample Size and Power

The planned sample size is 160 participants, randomized in a 1:1:1:1 ratio to each of the dose groups (placebo and SAGE-324: 15 mg, 30 mg, and 60 mg), stratified by baseline propranolol use, with at least 104 (65%, 26 participants per dose group) monotherapy participants and up to 56 (35%, 14 participants per dose group) adjunct therapy participants.

The sample size of 104 participants for the monotherapy cohort assumes a change from baseline at Day 91 in TETRAS upper limb Item 4 score for the placebo group of -1.2 points, a maximum decrease of -3.2 points from Baseline for a dose response in the 15-60mg dose groups with a standard deviation of 2.5.

Under these assumptions with a few prespecified candidate dose-response models, including linear, loglinear, quadratic, exponential, logistic, Emax, sigEmax, and beta as shown in Figure 2 (see Section 8.3.3.1 of this analysis plan for underlying parameters associated with each model), a sample size of 22 evaluable participants per group would provide 80% power for demonstrating a nonflat dose-response relationship by Multiple Comparisons Procedure - Modeling (MCP-Mod) approach, using a 1-sided type I error rate of 0.05.

Assuming a nonevaluable rate of 15% across all treatment groups, approximately 104 participants (26 per treatment group) will be randomized. Additional participants may be enrolled if the overall nonevaluable rate is higher than 20%.

The sample size for the adjunct therapy cohort is not based on statistical significance, but clinical considerations. Up to 56 adjunct therapy participants (14 per dose group) are to provide some adjunct therapy directional data on both efficacy and safety measures.

A blinded interim look of the primary and secondary endpoint data may be conducted to evaluate the sample size assumptions. Additional participants may be randomized if the

variances are larger than the assumptions above. However, no more than 200 participants, including adjunct therapy participants, will be randomized.

Figure 2: Prespecified Dose Response Models

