5.3. Randomization

This is a randomized, double-blind, placebo-controlled study. Participants will be randomized in a 1:1:1:1 ratio to treatment groups (15 mg, 30 mg, 60 mg SAGE-324, or placebo), stratified by baseline propranolol use. Randomization schedules will be generated by an independent statistician, and randomization to treatment group according to the randomization schedule will be performed centrally via an interactive response technology system.

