6. MODIFICATIONS

6.1. Modifications from the Approved Clinical Study Protocol

Protocol Amendment 3 (Version 4.0 dated 07-Oct-2022) permitted alcohol consumption with restrictions on amount and timing with respect to scheduled study visits. The summarization and main analysis of the primary endpoint will be repeated for categories of whether alcohol historically helped tremor (see Section 8.3.3.4).

Protocol Amendment 4 (Version 5.0 dated 10-Jan-2023) included an update to eligibility criteria and statistical analyses to include participants who are receiving propranolol for the treatment of essential tremor.

- Objectives and endpoints were updated to include the monotherapy cohort (SAGE-324), adjunct therapy cohort (SAGE-324 + propranolol), and overall population.
- Sample size and power were updated to focus on required enrollment for monotherapy participants; the adjunct therapy cohort was not based on statistical significance, but clinical considerations.
- Randomization was stratified by baseline propranolol use.
- Summarization and analysis of the primary efficacy variable, secondary efficacy variables was updated to be performed for the monotherapy cohort (primary cohort), adjunct therapy cohort (for directional investigation, excluding MCP-Mod analysis), and overall.

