The primary endpoint will be analyzed using a mixed effects model for repeated measures (MMRM); the model will include treatment, baseline TETRAS Performance Subscale Item 4 (upper limb tremor) total score, assessment timepoint, and timepoint-by-treatment as explanatory variables. All explanatory variables will be treated as fixed effects. All postbaseline clinic visits will be included in the model. An unstructured covariance structure will be used to model the within-participant errors. The Kenward-Roger approximation will be used to estimate denominator degrees of freedom. If there is a convergence issue with the unstructured covariance model, Toeplitz or Autoregressive (1) [AR(1)] covariance structure will be used, following this sequence until convergence is achieved. When the covariance structure is not unstructured, the sandwich estimator for the variance covariance matrix will be derived, using the EMPIRICAL option in the PROC MIXED statement in SAS. A pairwise comparison of change from baseline in TETRAS Performance Subscale Item 4

(upper limb tremor) for each SAGE-324 treatment group versus placebo will be provided. The p-values are not adjusted for multiplicity, so should be interpreted as nominal.

After the MMRM analysis by PROC MIXED, the estimated mean and covariance matrix at Day 91 will be passed to the MCP-Mod analysis (Bretz F, Pinheiro JC, Branson M, 2005) to test the dose-response relationship. A critical value will be determined from the joint multivariate normal distribution of the contrast test statistics at the overall one-sided alpha level of 0.05. If the test statistic exceeds this critical value, a nonflat dose-response relationship will be demonstrated.

In the analysis, multiple dose-response candidate models will be considered, including linear, loglinear, quadratic, exponential, logistic, Emax, sigEmax, and beta. In the trial design stage, these pre-specified candidate models based on available information were included in the MCP-Mod procedure. The parameters used to determine the contrast for testing assumes a change from baseline in TETRAS Item 4 upper limb total score in the placebo group of -1.2 points, a maximum decrease of -3.2 points from baseline for a dose response in the 15 to 60-mg dose groups. These can be done using the DoseFinding Package in R.

```
doses <-c(0, 15, 30, 60)
pboeff <- -1.2
acteff <- -2
quad <- guesst (d=45, p=1, 'quadratic')
exp <- guesst (d=45, p=0.5, 'exponential', Maxd=60)

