8.3.4. Analysis of Secondary Efficacy Variables

Summarization and analysis of the secondary efficacy variables will be performed for the monotherapy cohort (main analysis), adjunct therapy cohort (for directional investigation, excluding MCP-Mod analysis), and overall.

The primary, sensitivity, supportive, and subgroup analyses performed for the primary endpoint will be repeated for the secondary endpoint, change from baseline in TETRAS ADL composite score.

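### The overall (monotherapy plus adjunct) MMRM leaves out baseline propranolol use, the only stratification factor; a minor flaw that is nearly free to correct

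*SAP*

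**What the plan says.** SAP 5.3 randomises participants 1:1:1:1, "stratified by baseline propranolol use". No other stratification factor is named there, in SAP 5.1 and 5.2, or in Protocol 7.3 and 9.5. SAP 5.2 allows "up to 56 (35%, 14 participants per dose group) adjunct therapy participants", alongside at least 104 monotherapy participants.

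SAP 8.3.3 analyses the primary variable in the monotherapy cohort, "adjunct therapy cohort (for directional investigation, excluding MCP-Mod analysis), and overall". SAP 8.3.4 repeats this for the secondary variable, and the imputation sensitivity analysis in SAP 8.3.3.2 is also run on the overall Full Analysis Set.

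One MMRM is given. SAP 8.3.3.1 lists treatment, the baseline Item 4 "total score, assessment timepoint, and timepoint-by-treatment as explanatory variables". The model line in Appendix C has the same four terms. No visible passage adds propranolol use for the overall run, or for its Per Protocol and imputation repeats. The model in Protocol 13.5 has no such term either. The visible MCMC step in Appendix C imputes from treatment, baseline and visit scores only. The variable list of the second imputation step is not visible, so nothing is said about it here.

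**The concern.** A model should normally contain the factor by which the trial randomises. Stratified allocation removes between-arm variation in propranolol use. If the factor predicts change and is left out, the model still counts that variation as residual error. Its standard errors then exceed the true sampling error, and tests fall below their nominal level.

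The cohorts differ by design: one takes stable propranolol and must still reach the same Item 4 threshold. A non-zero D is therefore plausible, although the baseline score may absorb part of it.

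At stake are the overall estimates' standard errors, confidence intervals and nominal p-values. An overall MCP-Mod run would inherit the same covariance matrix. The SAP's MCP-Mod exclusion is attached to the adjunct cohort only, but no display title names an overall run, so that consequence is conditional. If dropout differs by arm and stratum, the balance argument fails and the pooled contrasts can be slightly biased.

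**Working it through.** **The plan's own figure.** With the eight candidate shapes in SAP 8.3.3.1, a maximum effect of 2.0 points (−3.2 against −1.2), SD 2.5 and one-sided 0.05, a Monte Carlo calculation at 22 per arm gives a mean power of 82.4%, consistent with the stated 80%. Then 22/0.85 = 25.9, which rounds up to 26 per arm, or 104. These figures concern the monotherapy cohort only, where propranolol use is constant.

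**Inputs.** SD 2.5 and adjunct share p = 56/160 = 0.35 come from SAP 5.2. D, the adjunct minus monotherapy difference in mean Day 91 change, is not in the documents and is assumed. D = 2.0 equals the whole assumed drug effect and is extreme.

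**1. Balanced strata.** Omitting the factor adds p(1−p)D² to the residual variance, so the standard error ratio is r = √(1 + p(1−p)D²/6.25). The one-sided size is 1 − Φ(1.645 r). At p = 0.35, p(1−p) = 0.2275. At D = 2, r = √(1 + 0.91/6.25) = 1.070.

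| Assumed D | SE inflation, 35% adjunct | One-sided size | SE inflation, 20 of 124 adjunct (16%, assumed) |
|---|---|---|---|
| 0 | 0% | 0.050 | 0% |
| 0.5 | 0.5% | 0.049 | 0.3% |
| 1.0 | 1.8% | 0.047 | 1.1% |
| 1.5 | 4.0% | 0.044 | 2.4% |
| 2.0 | 7.0% | 0.039 | 4.2% |

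The documents give no SD for the ADL composite. The same inflation applies at D/SD = 0, 0.2, 0.4, 0.6 and 0.8.

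A simulated Day 91 ANCOVA (22 monotherapy and 12 adjunct per arm, D = 2) agrees. The mean model standard error for 60 mg against placebo was 0.652 without the stratum and 0.608 with it, against a true sampling SD of 0.604. A two-sided 5% test rejected 3.2% and 4.6% of the time.

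**2. Main effect or interaction with timepoint.** Eight post-baseline visits, complete data, D = 2 at Day 91, and within-person correlation either compound symmetric at 0.6 or autoregressive at 0.85 (both assumed). If D grows linearly to Day 91, a single constant propranolol term still leaves 1.4–1.5% inflation, against 7.0% with no term. If D then vanishes by Day 97, 2.3–4.5% remains. In 20,000 trials per case, the size of a linear trend test was 0.037–0.040 with no term, 0.041–0.051 with a constant term and 0.048–0.051 with the timepoint interaction.

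**3. Even dropout.** SAP 5.2 is the source of the 15% rate: "Assuming a nonevaluable rate of 15% across all treatment groups". With 15% dropout everywhere, inflation is 1.9% at D = 1 and 7.3% at D = 2 (size 0.048 and 0.040). With the timepoint interaction, size is 0.049 and 0.052.

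**4. Uneven dropout (assumed).** Suppose 50% drop out in the 60 mg adjunct cell and 15% elsewhere. Adjunct participants then make up 7/(22.1 + 7) = 24.1% of 60 mg completers, against 11.9/34 = 35% on placebo. A completer contrast is biased by (0.241 − 0.35)D, about −0.11 at D = 1 and −0.22 at D = 2. An MMRM uses the earlier visits and gives about −0.09 and −0.17. Its trend-test size is 0.067 and 0.075 at D = +1 and +2, and 0.033 and 0.021 at D = −1 and −2. With propranolol-by-timepoint, bias is within 0.01 and size is 0.048–0.051.

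At a milder 30% in that cell, the adjunct share is 9.8/31.9 = 30.7%. The completer bias is about −0.04 at D = 1 and −0.09 at D = 2, with simulated size of about 0.055–0.059.

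**The case against.** The strongest reply is that little depends on this. The visible efficacy objectives, the estimand and the power calculation are monotherapy-only. On the pairwise comparisons the SAP says "The p-values are not adjusted for multiplicity, so should be interpreted as nominal". Each cohort is also reported separately, so a reader sees the within-stratum results. D is unknown, 35% is a ceiling, and up to D = 1 the inflation is below 2%. While the strata stay balanced, the error works against the drug. The 50% dropout case concerns one cell of 14 people and is far from the plan's uniform 15%. All of this stands and limits the point to a minor one.

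Two points of wording also stand. Parts of the SAP are withheld, and SAP 6.1 says that objectives were extended to the overall population, so absence can be claimed only for the visible text. An overall MCP-Mod run is an inference.

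It can also be said that a propranolol main effect is enough, since the SAP enters baseline score without a timepoint interaction. A main effect does recover most of the loss. The interaction recovers the remainder when D changes over visits, and its cost is small. None of these replies gives a reason to report a pooled analysis that ignores the randomisation stratum.

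**Conclusion.** The point holds. The visible overall MMRM omits the only stratification factor. If D is not zero and the strata stay balanced across arms in the Day 91 data, pooled standard errors are too large: by 0.5% to 7.0% for an assumed D of 0.5 to 2.0 points at a 35% adjunct share, and by less at a smaller share. If D is zero there is no effect.

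Under dropout that differs by arm and stratum, the conservatism can be lost. A small bias can then appear, in a direction set by the sign of D. That result rests on assumed dropout rates, and the largest figures come from a deliberately extreme case.

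The monotherapy primary and secondary analyses, their type I error and the sample size are untouched. The change should be made, but as a minor improvement to supportive results.

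**What to change.** Add to SAP 8.3.3 and 8.3.4:

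> For the overall analyses of the primary and secondary endpoints, including the Per Protocol Set and multiple-imputation repeats, the MMRM will additionally include baseline propranolol use (yes/no) and its interaction with assessment timepoint as fixed effects. Every step of the overall imputation model will include baseline propranolol use. In subgroup runs, these terms will be dropped only where they are not estimable.

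In Appendix C, for the overall run only:

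`Model CHG = BASE PROP PROP*AVISITN TRTP AVISITN TRTP*AVISITN`

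Code `PROP` as 0/1 and keep it out of the `CLASS` statement, so that LS means are evaluated at the average of `PROP`. In the MCMC step, add `PROP` to the `Var` list with one more `.` in each of `min`, `max` and `round`. Include `PROP` in the second imputation step as well. Leave the monotherapy and adjunct cohort models unchanged.

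The cost is one stratum effect per post-baseline TETRAS visit, eight parameters in all, for a variable already collected for randomisation. Only SAP wording and code for the overall run change.

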8.3.3.1. Primary Analysis

The estimand for the primary efficacy endpoint is defined as follows:

- There are 4 treatment groups for the monotherapy participants to be evaluated: SAGE-324 (15 mg, 30 mg, 60 mg) and placebo.
- The target population consists of the monotherapy participants aged 18 to 80 years and have a diagnosis of ET with combined total upper limb TETRAS Performance Subscale Item 4 of at least 12 with the dominant upper limb score of at least 6 and baseline TETRAS ADL score of at least 20.
- The outcome for the primary efficacy endpoint is the change from baseline in TETRAS Performance Subscale Item 4 score on Day 91 in the monotherapy cohort.
- The population-level summary measure is the dose-response of different doses of SAGE-324 and placebo for the monotherapy cohort.
- The treatment/hypothetical policy strategy will be adopted for the primary endpoint. For data collected after the intercurrent events, such as rescue medication, the treatment policy strategy will be used. For data not available after the intercurrent events, like premature discontinuation of study treatment, the hypothetical policy strategy will be adopted. This means that the dose-responses of different dose groups will be analyzed using all observed on-study data, using appropriate visit mapping specified in Table 2, regardless of the occurrence of the intercurrent event, including use of additional medication, premature discontinuation of treatment for any reason, or other protocol violations.

The observed value, change from baseline, and percent change from baseline of the TETRAS Performance Subscale Item 4 (upper limb tremor) scores (individual and total score by side and combined) will be summarized descriptively by randomized treatment at each scheduled time point.

The primary endpoint will be analyzed using a mixed effects model for repeated measures (MMRM); the model will include treatment, baseline TETRAS Performance Subscale Item 4 (upper limb tremor) total score, assessment timepoint, and timepoint-by-treatment as explanatory variables. All explanatory variables will be treated as fixed effects. All postbaseline clinic visits will be included in the model. An unstructured covariance structure will be used to model the within-participant errors. The Kenward-Roger approximation will be used to estimate denominator degrees of freedom. If there is a convergence issue with the unstructured covariance model, Toeplitz or Autoregressive (1) [AR(1)] covariance structure will be used, following this sequence until convergence is achieved. When the covariance structure is not unstructured, the sandwich estimator for the variance covariance matrix will be derived, using the EMPIRICAL option in the PROC MIXED statement in SAS. A pairwise comparison of change from baseline in TETRAS Performance Subscale Item 4

(upper limb tremor) for each SAGE-324 treatment group versus placebo will be provided. The p-values are not adjusted for multiplicity, so should be interpreted as nominal.

After the MMRM analysis by PROC MIXED, the estimated mean and covariance matrix at Day 91 will be passed to the MCP-Mod analysis (Bretz F, Pinheiro JC, Branson M, 2005) to test the dose-response relationship. A critical value will be determined from the joint multivariate normal distribution of the contrast test statistics at the overall one-sided alpha level of 0.05. If the test statistic exceeds this critical value, a nonflat dose-response relationship will be demonstrated.

In the analysis, multiple dose-response candidate models will be considered, including linear, loglinear, quadratic, exponential, logistic, Emax, sigEmax, and beta. In the trial design stage, these pre-specified candidate models based on available information were included in the MCP-Mod procedure. The parameters used to determine the contrast for testing assumes a change from baseline in TETRAS Item 4 upper limb total score in the placebo group of -1.2 points, a maximum decrease of -3.2 points from baseline for a dose response in the 15 to 60-mg dose groups. These can be done using the DoseFinding Package in R.

```
doses <-c(0, 15, 30, 60)
pboeff <- -1.2
acteff <- -2
quad <- guesst (d=45, p=1, 'quadratic')
exp <- guesst (d=45, p=0.5, 'exponential', Maxd=60)
emax <- guesst(d=30, p=0.8, 'emax')</pre>
sigemax <- guesst (d=c(15, 30), p=c (0.6, 0.8), 'sigEmax')</pre>
logis <- guesst (d=c(10, 45), p=c( 0.2, 0.8), model='logistic')
beta<- guesst(d=30, p=0.8, model='betaMod', dMax=45, scal=65, Maxd=60)</pre>
my.model <-Mods(linear=NULL,</pre>
                   linlog=NULL,
                  quadratic=quad,
                   exponential=exp,
                   emax=emax,
                   sigEmax=sigemax,
                   logistic=logis,
                   betaMod=beta,
                   doses=doses,
                   placEff=pboeff,
                   maxEff=acteff)
plot(my.model)
```

The optimal contrast coefficients are used to identify the best matching model, which can be computed with "optContr" function. It requires input of matrix. In this example it uses the covariance matrix exported from SAS, using repeated measurement analysis (MMRM) by PROC MIXED.

ContMatnew <- optContr(my.model, S=cov)

Model-specific contrast tests with null hypotheses of a flat dose-response curve are performed by "MCTtest" function. Any model that has t-statistics > critical value is statistically significant.

After the MCT test, if any model is significantly different from a flat dose-response curve, the best fit model could be selected.

Statistical Analysis Plan Methods Version 1.0 17-Jun-2024 Protocol Number: 324-ETD-202 (Version 6.0 2 November 2023)

plot(fit.xxx, CI=TRUE, plotData='meanCI', level=0.95)

The main comparison will be between SAGE-324 and placebo at Day 91, if a non-flat doseresponse relationship is established. Model-based point estimates (ie, least squares mean, 95% confidence intervals, and p-values) will be reported where applicable. Line plots of model-based LS Means and standard errors (SE) over time will be prepared for the primary endpoint.

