16.2.4.2.2	Essential Tremor Disease History
16.2.4.3.1	Prior Medications
16.2.4.3.2	Concomitant Medications
16.2.5.1	Study Drug Dispensation and Return
16.2.5.2	Study Drug Administration
16.2.5.3	Study Drug Exposure and Adherence
16.2.6.1.1	Essential Tremor Rating Assessment Scale (TETRAS) – Performance Subscale Item 4 (Upper Limb)
16.2.6.1.2	Essential Tremor Rating Assessment Scale (TETRAS) – Performance Subscales
16.2.6.1.3	Essential Tremor Rating Assessment Scale (TETRAS) – Activities of Daily Living

16.2.7.1	Adverse Events
16.2.7.2	Serious Adverse Events (Safety Set)

- 16.2.7.3 Listing of Deaths (Safety Set)
- 16.2.7.4 Adverse Events Leading to Treatment Discontinuation (Safety Set)
- 16.2.7.5 Adverse Events Leading to Study Discontinuation (Safety Set)
- 16.2.8.1.1 *Clinical Chemistry*
- 16.2.8.1.2 Clinical Hematology
- 16.2.8.1.3 Clinical Coagulation
- 16.2.8.1.4 Urinalysis

- 16.2.8.2.1 Pregnancy Test
- 16.2.8.2.2 FSH Testing
- 16.2.8.2.3 Drug Screen
- 16.2.8.2.4 Alcohol and Cotinine Screen
- 16.2.8.3 12-Lead Electrocardiogram (ECG)
- 16.2.8.4 Vital Signs
- 16.2.8.5 Physical Examinations
- 16.2.8.6 Mental Status Examination
- 16.2.8.7 Abbreviated Neurological Examination

Phone Call During Treatment and Follow-up Period 16.2.8.9

Figures

14.2.1.1.1	Least Squares Mean Change from Baseline in TETRAS Performance Subscale Item 4 (Upper Limb Tremor) Score by Time Point (Full Analysis Set)
14.2.1.1.2	Forest Plot of Change from Baseline in TETRAS Performance Subscale Item 4 (Upper Limb Tremor) Score at Day 91, Total Score (Full Analysis Set)
14.2.1.1.3	Dose Response for TETRAS Performance Subscale Item 4 (Upper Limb Tremor) Score at Day 91, Total Score (Full Analysis Set)
14.2.1.2.1	Least Squares Mean Change from Baseline in TETRAS Performance Subscale Item 4 (Upper Limb Tremor) Score by Time Point (Per Protocol Set)
14.2.1.2.2	Dose Response for TETRAS Performance Subscale Item 4 (Upper Limb Tremor) Score at Day 91, Total Score (Per Protocol Set)
14.2.2.1.1	Least Squares Mean Change from Baseline in TETRAS ADL Composite Score by Time Point (Full Analysis Set)
14.2.2.1.2	Forest Plot of Change from Baseline in TETRAS ADL Composite Score at Day 91, Total Score (Full Analysis Set)
14.2.2.1.3	Dose Response for TETRAS ADL Composite Score at Day 91, Total Score (Full Analysis Set)
14.2.2.2.1	Least Squares Mean Change from Baseline in TETRAS ADL Composite Score by Time Point (Per Protocol Set)

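### After a positive MCP test, the SAP plots one 'best fit' dose-response curve with a 95% band but names no selection rule and makes no allowance for selection; at 15 and 30 mg the band can under-cover.

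*SAP*

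**What the plan says.** SAP 8.3.3.1 passes the Day 91 means and covariance from the MMRM to MCP-Mod. The candidate set has eight shapes, "including linear, loglinear, quadratic, exponential, logistic, Emax, sigEmax, and beta", for the four doses 0, 15, 30 and 60 mg. Once a contrast is significant, "if any model is significantly different from a flat dose-response curve, the best fit model could be selected". The code then plots a single fitted object: "plot(fit.xxx, CI=TRUE, plotData='meanCI', level=0.95".

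No rule for choosing the best fit is given. The nearest hint is a sentence that uses the optimal contrasts to find the best matching model. Neither document mentions model averaging, a bootstrap or any other allowance for selection.

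The curve is a planned output. SAP Appendix D lists "Dose Response for TETRAS Performance Subscale Item 4 (Upper Limb Tremor) Score at Day 91, Total Score (Full Analysis Set", the same figure for the Per Protocol Set, and one for the ADL composite. SAP 8.3.4 repeats the primary analyses for that secondary endpoint.

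Separately, 8.3.3.1 reports each dose against placebo from the MMRM. Those estimates do not use the selected curve.

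**The concern.** Two things are left open. First, the analyst can choose the criterion after unblinding, and different criteria give different curves. Second, a model-based interval computed after selection describes only the uncertainty inside the chosen model. If that model is simpler than the truth, the interval is both misplaced and too short.

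The primary objective is the dose-response relationship, and Protocol 5.1 says the dose range was chosen to find the best balance of efficacy and tolerability. A band that is too narrow at 15 and 30 mg would overstate how much the trial has learned about the lower doses.

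**Working it through.** **Inputs from the SAP.** Section 5.2: "a sample size of 22 evaluable participants per group"; "dose groups with a standard deviation of 2.5"; placebo change -1.2 and largest change -3.2, so a maximum effect of -2; a test "using a 1-sided type I error rate of 0.05". Section 8.3.3.1: the doses and the guesses that fix the eight shapes.

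**Assumptions not in the documents.** Loglinear offset 0.6, beta scale 72 in the model set, the R package's usual parameter bounds, and independent group means.

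**Step 1: reproduce the plan's power.** The SE of a group mean is 2.5/√22 = 0.533. The joint critical value for the eight contrasts is 1.96. As a hand check for a linear truth (effects 0, -0.5, -1, -2; mean -0.875), the sum of squared deviations is 2.1875. The noncentrality is then √2.1875/0.533 = 2.77, and the linear contrast alone has power Φ(2.77 - 1.96) ≈ 0.79. Taking the maximum over all eight contrasts, power runs from 79.9% (beta) to 87.2% (exponential), mean 85.1%. The minimum matches the SAP's claim that the design "would provide 80% power for demonstrating a nonflat dose-response relationship". If the beta scale were 65 throughout, the minimum would be 66% and the mean 83%.

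**Step 2: parameters per model.** Linear 2, loglinear 2; quadratic 3, exponential 3, Emax 3; sigEmax 4, logistic 4, beta 4 (scale fixed). Three of the eight have as many parameters as there are dose groups.

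**Step 3: coverage of the plotted band.** For each of the eight planned shapes, 20,000 trials were simulated and kept if the MCP test was significant. All eight models were fitted, one was selected, and I counted how often its delta-method 95% band contained the true mean. Figures are averages over shapes, with the range in brackets.

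| Selection rule | 15 mg | 30 mg |
|---|---|---|
| AIC | 86% (80-92) | 87% (82-91) |
| Largest contrast statistic | 92% (91-95) | 93% (92-94) |
| Smallest residual (smaller runs, range only) | 93-97% | 93-96% |
| MMRM LS-mean interval, no model | 94-96% | 94-96% |

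Smaller repeat runs, with 1,000 to 1,500 significant trials per shape, widen the ranges to 80-93% for AIC and about 90-96% for the largest statistic. At 0 and 60 mg the averages are 93-95% under both of those rules.

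**Step 4: the effect read off the curve.** For 15 mg minus placebo, average coverage is 73% under AIC and 83% under the largest statistic. It is lowest when the truth is exponential: about 36-41% under AIC and 57-66% under the largest statistic across runs.

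**Step 5: where the shortfall comes from.** AIC picks a two-parameter linear or loglinear model in 63-87% of trials and a four-parameter model in only 2-10% (mean 4%). The largest statistic picks a four-parameter model in 19-48% (mean 30%).

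A linear fit shows the mechanism. With mean dose 26.25 and Sxx = 1968.75, the SE of the fitted mean at 15 mg is 0.533 × √(1/4 + 11.25²/1968.75) = 0.299. The 95% half-width is 0.59, against 1.96 × 0.533 = 1.04 for the LS mean. For 15 mg minus placebo the linear fit's SE is 15 × 0.533/√1968.75 = 0.180, half-width 0.35, against 1.96 × 0.533 × √2 = 1.48 for the two LS means.

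Suppose the truth is the SAP's exponential shape (delta 24.6; effects 0, -0.161, -0.456, -2). The expected slope is then -67.4/1968.75 = -0.0342, so the line puts the 15 mg effect at -0.51 instead of -0.16. That error of 0.35 equals the half-width, so a straight-line fit would cover the true 15 mg effect only about half the time, even before any conditioning on selection.

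**The case against.** The strongest reply is that the curve is a secondary display. The wording is permissive (the model *could* be selected), the hypothesis test comes first, and the dose-versus-placebo results come from the MMRM, whose mean intervals cover 94-96% in the same trials. The SAP never mentions AIC. Under the contrast-based rule that its text hints at, the band falls short by only 2-3 points on average. All of this stands, and it limits the point to an improvement in estimation.

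A reader might go further in four ways that the documents and the calculations do not support:

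- *That the band is too narrow whatever the rule.* Under smallest residual it is close to nominal at both lower doses.
- *That the four-parameter models cause the shortfall.* AIC picks them least and covers worst. Smallest residual picks them most (77-88% of trials in a run of four of the shapes) and its band covers best. Saturation is a separate matter: such a fit leaves no degrees of freedom to check the shape.
- *That 73-83% is the coverage of the plotted band.* Those figures are for a difference from placebo read off the curve, and neither document says that such an interval will be reported.
- *That this figure will decide the dose.* No passage says so.

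**Conclusion.** The point holds as a gap in prespecification with a measurable consequence. The SAP selects one of eight models by an unnamed rule and attaches a band that ignores the selection. Depending on the rule, coverage at 15 and 30 mg runs from near nominal down to an average of about 86-87%, with individual shapes as low as 80%. Dose differences taken from the curve fare worse.

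The figures are conditional on a significant MCP test. They rest on the SAP's planning values, on the true shape being one of its eight candidates, and on the software settings listed as assumptions in the working.

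The change should be made but is not critical, because the primary conclusion does not depend on it.

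**What to change.** In SAP 8.3.3.1, and through it 8.3.4, replace the best-fit sentence with a named criterion, for example lowest generalized AIC. Obtain the curve and its 95% band by bootstrap:

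1. Draw at least 1,000 samples from the multivariate normal distribution of the Day 91 LS means and covariance.
2. Refit the candidates and repeat the selection in each draw.
3. Report the median and the 2.5 and 97.5 percentiles.

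All eight candidates may stay; a limit to three parameters in this step is optional. Label any single-model fit as descriptive.

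With all eight kept (2,000 significant trials per shape, 300 draws each), this gave average band coverage of about 96% at every dose, with a lowest shape of 94.5% at 15 and 30 mg. For 15 mg minus placebo it averaged about 97%. AIC-weighted averaging with a bootstrap is a workable alternative: 94% on average and 92% at worst at 15 and 30 mg.

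The cost is SAP wording, a short R loop and slightly wider intervals. The MCP test, its alpha and the MMRM comparisons do not change.
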